## 3. STUDY DESIGN

### 3.1 Study Design

This study is a Phase 2, multicenter, randomized, double-blind, placebo-controlled study to evaluate the efficacy and safety of imsidolimab in adult subjects with hidradenitis suppurativa (HS). This study will also characterize the pharmacokinetic (PK) profile of imsidolimab and explore the immune response to imsidolimab in subjects with HS.

To be eligible for this study, subjects must have a clinically confirmed diagnosis of HS with a disease duration of at least 6 months before Day 1. In addition, subjects will have the following characteristics at Screening and Day 1:

- 1) HS lesions present in at least 2 distinct anatomical areas, 1 of which must be Hurley Stage II (i.e., single or multiple, widely separated, recurrent abscesses with tract formation and cicatrization) or Hurley Stage III (i.e., diffuse or near diffuse involvement, or multiple interconnected tracts and abscesses across the entire area);
- 2) total abscess and inflammatory nodule (AN) count of  $\geq 5$ ;
- 3)  $\leq 20$  draining fistulas.

Randomization will be stratified based on Hurley Stage at baseline (Stage II or III).

The maximum study duration per subject is approximately 44 weeks, which includes a screening period of up to 30 days, followed by a 16-week placebo-controlled period, a 16-week treatment extension period, and an 8-week follow up period. The placebo-controlled period ends at Day 113 (Week 16) and the treatment extension period starts when study treatment is administered at the Week 16 visit. Of note, during the extension period all subjects will receive imsidolimab but their treatment will remain blinded.

During the placebo-controlled period, eligible subjects will be randomized (1:1:1) to receive either imsidolimab (at 1 of 2 different regimens) or placebo, subcutaneously (SC) administered on 4 occasions: Day 1, Day 29 (Week 4), Day 57 (Week 8), and Day 85 (Week 12).

The treatment arms during the placebo-controlled period will be as follows:

[figure not shown]
- Imsidolimab 400 mg on Day 1, followed by 200 mg on Days 29, 57, and 85
- Imsidolimab 200 mg on Day 1, followed by 100 mg on Days 29, 57, and 85
- Placebo on Days 1, 29, 57, and 85

During the extension period, all subjects will receive imsidolimab, SC administered on 4 occasions:

- 400 mg dose of imsidolimab on Day 113 for subjects assigned to placebo arm 3A during the placebo-controlled period, followed by 200 mg doses on Days 141, 169, and 197

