- **Proportion of subjects achieving “A little bothered” or “Not at all bothered” for the PGI-B at each visit**

For each treatment group, the number of subjects “A little bothered” or “Not at all bothered” for the PGI-B will be calculated at each visit specified in the Schedule of Activities in **Section 3.6**. The proportion of such subjects will be calculated for each treatment group at each visit as:

$$\frac{\text{\# of subjects in treatment group achieving either “A little bothered” or “Not at all bothered” category at Week } x}{\text{\# of subjects in treatment group with PGI-B data at Week } x}$$

- **Proportion of subjects in each response category for the PGI-S at each visit**

The Patient Global Impression of Severity (PGI-S) is a single-item question, which asks the patient to rate the current severity of the HS (“No Activity” / “Clear Skin”, “Mild”, “Moderate”, and “Severe”).

For each treatment group, the number of subjects in each response category for the PGI-S will be calculated at each visit specified in the Schedule of Activities in **Section 3.6**. The proportion of such subjects will be calculated for each treatment group at each visit as:

$$\frac{\text{\# of subjects in treatment group in each response category at Week } x}{\text{\# of subjects in treatment group with PGI-S score at Week } x}$$

- **Change from Baseline in PGI-S at each visit**
- **Proportion of subjects achieving “Mild” or “No activity” / “Clear skin” for the PGI-S at each visit**

For each treatment group, the number of subjects with either “Mild” or “No activity” / “Clear Skin” response category for the PGI-S will be calculated at each visit specified in the Schedule of Activities in **Section 3.6**. The proportion of such subjects will be calculated for each treatment group at each visit as:

$$\frac{\text{\# of subjects in treatment group with either "Mild" or "No activity" / "Clear Skin" response category at Week } x}{\text{\# of subjects in treatment group with PGI-S score at Week } x}$$

- **Proportion of subjects in each category of Hurley Stage at each visit**

The Hurley system describes 3 clinical stages of HS (Stage I, II, and III). The Hurley stage at a given visit will be determined by the site as the greatest Hurley Stage observed from all involved anatomical regions.

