## 7.5.3 Exploratory Efficacy Analyses

### Protocol Specified Exploratory Efficacy Analyses

The change from baseline in Hurley Stage, HS-PGA, HS-PtGA, PGI-B, and PGI-S will be summarized in shift tables. In the shift table, for each treatment, the counts and percentages will be shown for baseline values crossed with each post-baseline time point. Agreement between the baseline score and each post-baseline score will be estimated with a weighted Kappa coefficient and corresponding 90% CI (Cohen, 1968) A test of treatment difference for agreement will be done separately for each treatment group and will consist of a CMH test (ANOVA for row means) applied to a 2x2xR table (baseline Hurley Stage x treatment x agreement score), where the agreement score is the Cicchetti-Allison weight (Cicchetti, 1971) used for the weighted Kappa coefficient, which is  $1 - \text{difference}/(R-1)$  where R is the number of categories in the endpoint.

The change from baseline and percent change (shown as \*) from baseline in each continuous exploratory variable (AN count\*, abscess count, inflammatory nodule count, draining fistula count at each visit, calculated composite of abscess, inflammatory nodule and draining fistula count, calculated composite of abscesses, draining fistulas, and inflammatory and non-inflammatory nodules, HS Pain NRS\* at visits other than Week 16, worst HS pain NRS, DLQI scores at each visit, IHS4 score at each visit, HiSQOL score at each visit ) will be analyzed using a similar MMRM model as described for the primary efficacy analysis in **Section 7.5.1**, but changing baseline AN count to baseline of the outcome. Summary statistics and the results of statistical testing at each visit will be provided for each continuous exploratory variable.

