Combine Parameter Estimates for LSmeans	<pre> PROC MIANALYZE DATA=OUTREG;   BY VISIT;   MODELEFFECTS TRT; /* TRT IS THE VARIABLE FOR LS TREATMENT DIFFERENCES */   STDERR TRTERR; /* TRTERR IS THE STANDARD ERROR FOR TREATMENT DIFFERENCES */   RUN; </pre>
Cochran-Mantel-Haenszel ANOVA statistics (row means score)	<pre> PROC FREQ;   TABLES BASEHSSTAGE *TRT*X/CMH2 ALPHA=0.1 SCORE=RANK;   RUN; </pre> 
Where BASEHSSTAGE is randomized Hurley Stage, TRT is treatment, and X is the outcome variable.

Ordinal Logistic Regression using PROC LOGISTIC	<pre> PROC LOGISTIC;   CLASS TRT BASE;   MODEL Y = TRT BASE;   RUN; </pre> 
Where Y is the ordinal outcome variable, TRT is treatment, BASE the baseline of outcome variable.

Exact unconditional CI	<pre> PROC FREQ;   TABLES TRT*X;   EXACT OR;   RUN; </pre>

Test	Template SAS Code for Modeling (SAS Version 9.4)
	Where TRT is treatment, and X is the outcome variable.
Obtaining generalized risk difference	<pre>PROC FREQ;   TABLES TRT*X / ALL LIST MISSING;   TEST SMDCR; RUN;</pre> 
Where TRT is treatment, and X is the outcome variable.

Weighted Kappa and confidence interval	<pre>PROC FREQ;   WEIGHT COUNT;   TABLES BASEHSSTAGE*TRT*X/AGREE ALPHA=0.1; RUN;</pre> 
Where BASEHSSTAGE is Hurley Stage at baseline, TRT is treatment, and X is the outcome variable.

Test of treatment difference for agreement	<pre>PROC FREQ;   TABLES BASEHSSTAGE*TRT*X/CMH2; RUN;</pre> 
Where BASEHSSTAGE is Hurley Stage at baseline, TRT is treatment, and X is the Cicchetti-Allison weight of outcome variable. Cicchetti-Allison weight = 1- abs(CHG)/(k-1), where k = number of categories of the outcome variable.

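### The SAP Appendix 2 template for weighted kappa crosses treatment arm with outcome, not baseline score with post-baseline score as SAP 7.5.3 plans

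*SAP*

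**What the plan says.** SAP 7.5.3 (Protocol Specified Exploratory Efficacy Analyses) names five ordinal endpoints: "The change from baseline in Hurley Stage, HS-PGA, HS-PtGA, PGI-B, and PGI-S will be summarized in shift tables". For each treatment, "the counts and percentages will be shown for baseline values crossed with each post-baseline time point". The statistic follows: "Agreement between the baseline score and each post-baseline score will be estimated with a weighted Kappa coefficient and corresponding 90% CI". The same paragraph gives the Cicchetti-Allison weights, and it plans a separate CMH test to compare agreement between arms.

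The SAP Appendix 2 entry titled Weighted Kappa and confidence interval has a `WEIGHT COUNT` statement and the request "TABLES BASEHSSTAGE*TRT*X/AGREE ALPHA=0.1". Its note reads: "Where BASEHSSTAGE is Hurley Stage at baseline, TRT is treatment, and X is the outcome variable".

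Appendix 2 presents its code as templates. It also says that the section is to be completed before the SAP is finally signed off. The SAP is V1.0 with a sign-off date of 16 August 2022.

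**The concern.** The text and the code describe different tables. In a three-way PROC FREQ request the first variable is the stratum and the last two form the table, so AGREE acts on TRT by X. Treatment arm takes the place of one of the two ratings. The baseline score of HS-PGA, HS-PtGA, PGI-B or PGI-S appears nowhere in the request. For Hurley Stage the baseline value appears only as the stratum and never as a row.

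Kappa measures agreement between two ratings on the same categories, so it needs a square table with matching axes. Arm by outcome is usually not square. When it is, the result says nothing about change from baseline. At stake are the kappa estimates and 90% CIs that accompany five exploratory shift-table analyses.

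**Working it through.** The documents give no kappa value to reproduce. The check has two parts: the shape of the coded table, then what the coded and planned tables return on the same counts.

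**Inputs.**
- Levels of X: Hurley Stage 3 (SAP 6.2.4); HS-PGA 5 (Protocol 8.1.8); HS-PtGA 5 (Protocol Appendix 6); PGI-B 5 (Protocol Appendix 4); PGI-S 4 (Protocol 8.1.2).
- Levels of TRT: 3 in the placebo-controlled period (SAP 3.1); 4 if the extension arms 1, 2, 3A and 3B are kept apart (SAP title page); 2 if comparisons are pairwise.

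**Shape of the coded TRT by X table, full scales.**

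| Endpoint | 2 arms | 3 arms | 4 arms |
|---|---|---|---|
| Hurley Stage | 2x3 | **3x3** | 4x3 |
| PGI-S | 2x4 | 3x4 | **4x4** |
| HS-PGA, HS-PtGA, PGI-B | 2x5 | 3x5 | 4x5 |

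Only the two bold tables are square. Run within a single arm, the table is 1xR and never square on the full scale. If some categories are not observed, a table can become square or stop being square by chance. It is still arm by outcome.

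**Value when the table is square.** All counts here are assumptions, chosen only to show behaviour. The weights are those of SAP 7.5.3, w = 1 - |i - j|/(R - 1). With R = 3 they are 1, 0.5 and 0. Kappa = (po - pe)/(1 - pe), where po and pe are the weighted observed and chance agreement.

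*Identical arms.* Suppose that in every arm 20 subjects start at Stage II and end at I/II/III as 6/12/2, and 16 start at Stage III and end as 1/5/10.
- Planned table, per arm (n = 36): po = (22 + 0.5 x 13)/36 = 0.792. pe = [20 x (3.5 + 17 + 6) + 16 x (8.5 + 12)]/36² = 858/1296 = 0.662. Kappa = 0.130/0.338 = 0.38.
- Coded table: the rows are the same in every arm, so po = pe and kappa = 0.00 in both strata.

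*Differing arms.* Suppose that in the Stage II stratum the three arms end as 10/8/2, 7/11/2 and 3/12/5 (n = 60).
- Coded: po = (26 + 0.5 x 29)/60 = 0.675. pe = (20 x 1.5 + 31 x 2 + 9 x 1.5)/180 = 0.586. Kappa = 0.089/0.414 = 0.21.
- Coded, arm order reversed: po = (16 + 0.5 x 29)/60 = 0.508 and pe is unchanged. Kappa = -0.078/0.414 = -0.19.
- Planned, per arm, with the Stage III row kept at 1/5/10: 0.33, 0.37 and 0.31. These do not depend on how the arms are ordered.

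*No change at all.* If every subject keeps the baseline stage, the planned kappa is 1.0. Each coded stratum collapses to a 3x1 table and returns nothing.

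**Shape of the planned table.** Inclusion criterion 3 requires a region at Stage II or III, and Protocol 8.1.9 assigns the subject the stage of the worst region. Baseline Hurley Stage is therefore II or III, while Stage I is possible later. A plain baseline by post-baseline table can then be 2x3, and kappa fails again unless the empty Stage I row is kept.

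**The case against.** The strongest reply is that SAP 7.5.3 already states the rows, columns, grouping, weights and CI level correctly, and that the code is a skeleton with no input dataset or visit variable. Blinded dry runs (SAP 3.4) and the programming quality-control plan (SAP 4) should expose a table that returns no kappa. The same layout is right for the CMH test listed directly below, where X is redefined as an agreement weight built from the change score. The kappa entry looks like a copy of that layout.

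Much of this stands, and it limits the weight of the point. It does not remove the contradiction. Appendix 2 was to be completed before sign-off, the SAP is signed off, and the entry defines its variables explicitly.

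A reader might infer three stronger things that the documents do not support:
- That there are never more than three treatment levels, so that PGI-S and the five-category scales can never give a square table. The four extension arms make PGI-S 4x4, and shape also depends on which categories are observed.
- That a wrong kappa will be reported. That would need a square table and a review that overlooks arm by outcome output placed beside correct shift tables.
- That the choice of analysis is at fault. The method in SAP 7.5.3 is not in question; only its code is.

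**Conclusion.** The point holds as an error in the template code. Run as written, the entry does not deliver the agreement statistic that SAP 7.5.3 describes. It yields either no kappa or an arm-versus-outcome value that depends on the order of the arms.

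Its reach is small. It concerns one exploratory descriptive statistic over five endpoints. The shift tables, the CMH test of agreement, and the primary and secondary analyses do not use this entry.

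The conclusion rests on standard PROC FREQ table order and on kappa's need for a square table. The code was not run in SAS. The numerical values rest on assumed counts and show behaviour, not expected results.

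**What to change.** Replace the Appendix 2 entry with:

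`PROC FREQ; BY TRT VISIT; WEIGHT COUNT / ZEROS; TABLES BASESCORE*POSTSCORE / AGREE ALPHA=0.1; RUN;`

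In the note, define BASESCORE as the endpoint's baseline score and POSTSCORE as its score at the visit. State that the input data carry a zero-count record for every scale category on both axes, so that each table is 3x3, 4x4 or 5x5. Hurley Stage needs this in particular, because its baseline Stage I row is normally empty.

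The cost is a few lines in one appendix entry plus a small data-preparation step for the zero-count records. No planned analysis changes.

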- Change from Baseline in PGIS at each visit
- Proportion of subjects in each category of Hurley Stage at each visit
- Change from Baseline in Hurley Stage at Weeks 16, 32, and 40
- Proportion of subjects achieving at least a 1-stage improvement in Hurley stage
- Skin tape strip and drainage fluid biomarkers analysis including, but not limited to, IL-36 and Th-17
- Presence of ADAs to imsidolimab
- Serum concentration following imsidolimab administration and other parameters as appropriate will be determined to describe the PK profile of imsidolimab

Methods for analyzing the above categorical and continuous efficacy endpoints will mirror the methods described in [Section 9.4.6.1](#) and [9.4.6.2](#), respectively. ITT analysis set will be used for analysis of exploratory efficacy endpoints.

As further additional exploratory analyses, the primary efficacy endpoint, all secondary efficacy endpoints, and some of the exploratory endpoints will be summarized using the Extension analysis population.

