The frequency and percentage of subjects for each categorical exploratory variable (proportion of subjects achieving AN50 and AN75 responses, percentage of subjects experiencing flare, proportion of subjects achieving HiSCR50 and HiSCR75 at each visit, proportion of subjects achieving HS-PGA of inactive (0) or almost inactive (1) at each visit, proportion of subjects achieving at least 2-point decrease in HS-PGA at each visit, proportion of subject with a 2 point reduction from baseline on HS-PGA at each visit, proportion of subjects achieving a 3-point reduction on the HS Worst Pain NRS for subjects with baseline HS Worst Pain NRS of at least 3, proportion of subjects achieving a 3-point reduction on the HS Average Pain NRS

for subjects with baseline HS Average Pain NRS of at least 3, proportion of subjects requiring rescue medication or treatment at each visit, proportion of subjects in each response category for the HS-PtGA at each visit, proportion of subjects in each response category for the PGI-C at each visit, proportion of subjects achieving much improvement in PGI-C at each visit, proportion of subjects achieving improvement at each visit, proportion of subjects in each response category for the PGI-S at each visit, proportion of subjects achieving “Mild” or “No activity” / “Clear skin” for the PGI-S at each visit, proportion of subject in each response category for the PGI-B at each visit, proportion of subjects achieving “A little bothered” or “Not at all bothered” for the PGI-B at each visit, proportion of subjects in each category of Hurley Stage at each visit, proportion of subjects achieving at least a 1-stage improvement (decrease) in Hurley Stage will be summarized at each visit.

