For PGI-S, PGI-B, HS-PtGA, HS-PGA, and PGI-C, the difference in distribution between the imsidolimab and placebo groups will be compared separately for each treatment group by using a Wilcoxon rank-sum test and Somers' d statistic, which may be interpreted as a generalized risk difference ([Edwardes, 2000](#)). This will be performed over all subjects for each comparison, and within each stratum for Hurley Stage. The difference in distribution between the imsidolimab and placebo groups (stratified by baseline Hurley Stage) will be compared using a Cochran-Mantel-Haenszel test as described in **Section 7.5.2.2**. For PGI-S, PGI-B, HS-PtGA, and HS-PGA, the change from baseline will also be analyzed using an ordinal logistic regression model with treatment and baseline Hurley Stage as categorical covariates. Odds ratios resulting from this model along with 90% CI will be reported. The proportional odds assumption will also be tested, and the corresponding p-value will be reported.

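### For change in Hurley Stage, the only treatment test the SAP names uses absolute change from baseline, so it cannot separate benefit from harm

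*SAP*

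**What the plan says.** SAP 7.5.3 puts change from baseline in Hurley Stage, HS-PGA, HS-PtGA, PGI-B and PGI-S into shift tables. It adds two analyses of agreement with baseline:

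- **Kappa.** "Agreement between the baseline score and each post-baseline score will be estimated with a weighted Kappa coefficient", with a 90% CI.
- **Treatment test.** "A test of treatment difference for agreement will be done separately for each treatment group and will consist of a CMH test". It is the row-mean form, stratified by baseline Hurley Stage, with the Cicchetti-Allison weight as the score. The 7.5.3 text writes the weight with a plain difference. Appendix 2 makes it absolute: "Cicchetti-Allison weight = 1- abs(CHG)/(k-1), where k = number of categories of the outcome variable".

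Directional tests follow in 7.5.3 for the other four scales: Wilcoxon rank-sum with Somers' d, a stratified CMH test, and a regression ("For PGI-S, PGI-B, HS-PtGA, and HS-PGA, the change from baseline will also be analyzed using an ordinal logistic regression model"). In those sentences Hurley Stage appears only as a stratum or covariate, and it is absent from the MMRM list as well. For the responder version, the SAP says only that the "proportion of subjects achieving at least a 1-stage improvement (decrease) in Hurley Stage will be summarized at each visit".

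Protocol 9.4.7 is broader: "Methods for analyzing the above categorical and continuous efficacy endpoints will mirror the methods described in" Sections 9.4.6.1 and 9.4.6.2. Section 9.4.6.1 compares arms on categorical endpoints with a CMH test adjusted for Hurley Stage. SAP Section 8 lists no departure from this.

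**The concern.** SAP 6.2.4 defines the endpoint as signed: Hurley Stage at the visit minus Hurley Stage at baseline, so a negative value is improvement. The named test drops the sign and asks whether the arms differ in how far subjects moved from baseline in either direction.

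Two things follow. First, lower agreement on imsidolimab can mean more improvement or more worsening, and neither the p-value nor the sign of the test statistic says which. Second, if imsidolimab subjects improve while placebo subjects worsen, both movements lower agreement and the contrast shrinks, although that is the pattern an effective treatment could produce.

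A separate slip concerns kappa. The text asks for agreement between baseline and post-baseline scores, but the template runs "TABLES BASEHSSTAGE*TRT*X/AGREE ALPHA=0.1", which crosses treatment with outcome within each Hurley stratum. Kappa from that table does not measure agreement with baseline.

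**Working it through.** The plan gives no power figure for this endpoint, so there is none to reproduce.

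**Inputs from the documents.** Hurley Stage has k = 3 categories (SAP 6.2.4). Baseline strata are Stage II and Stage III (SAP 3.2). The sample size assumes 36 evaluable subjects per arm at Week 16 (SAP 3.5). Alpha is 0.10 two-sided (SAP 7.5).

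**Step 1: the score.** With k = 3 the weight is 1 − |change|/2.

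| Change in stage | Agreement score |
|---|---|
| −2 (III to I) | 0 |
| −1 (II to I, or III to II) | 0.5 |
| 0 | 1 |
| +1 (II to III) | 0.5 |

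Stage III subjects can only stay or improve, so the ambiguity arises in the Stage II stratum. The CMH test pools both strata.

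**Step 2: worked tables.** Illustrative counts, 18 per arm per stratum, with 2/18 improving in each arm in Stage III. Per stratum, the numerator term is the active-arm score sum minus 18 times the pooled mean. The variance term is [18 × 18/(36 × 35)] × SS = 0.2571 × SS, where SS is the pooled sum of squares. Q is the squared total numerator over the total variance, on 1 df.

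*Benefit: 6/18 active vs 1/18 placebo go from II to I.*

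- Stage II numerator: 15 − 18 × (32.5/36) = 15 − 16.25 = −1.25.
- Stage II SS: 0.25 × 7 × 29/36 = 1.4097, variance 0.3625.
- Stage III numerator: 0. SS: 0.25 × 4 × 32/36 = 0.8889, variance 0.2286.
- Q = 1.5625/0.5911 = 2.644, p = 0.104.

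*Harm: 6/18 active vs 1/18 placebo go from II to III.* Every score is unchanged, so the numerator is again −1.25, Q = 2.644 and p = 0.104. With signed change the p-value is also 0.104 in both cases, but the numerator is −2.5 for benefit and +2.5 for harm.

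*Opposite movement: 6/18 active improve, 6/18 placebo worsen in Stage II.*

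- Agreement score: numerator 0, Q = 0, p = 1.00.
- Signed change: numerator −6. Variance is 0.2571 × 12 + 0.2571 × 3.5556 = 3.0857 + 0.9143 = 4.0. Q = 36/4 = 9.0, p = 0.0027.

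**Step 3: power.** 100,000 simulated trials per row, 36 per arm, 18 per stratum, two-stratum CMH mean-score statistic against 2.7055. The first four rows assume 35% (active) vs 10% (placebo) improving, without two-stage moves. The documents give no improvement or worsening rates; all are assumptions.

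| Stage II worsening, active vs placebo | Agreement score | Signed change |
|---|---|---|
| 0% vs 0% | 84% | 84% |
| 5% vs 5% | 81% | 77% |
| 5% vs 10% | 71% | 81% |
| 5% vs 20% | 51% | 89% |
| 5% vs 20%, 30% of subjects Stage III | 39% | 90% |
| 5% vs 20%, 70% of subjects Stage III | 64% | 87% |

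**Step 4: a harm case.** Let 10% improve in both arms and 45% (active) vs 5% (placebo) of Stage II subjects worsen. The agreement test rejects 71% of the time. Mean agreement, with half the subjects in each stratum:

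- Harm, active: (1 − 0.55/2 + 1 − 0.10/2)/2 = (0.725 + 0.95)/2 = 0.84.
- Harm, placebo: (0.925 + 0.95)/2 = 0.94.
- Benefit (35% vs 10% improving, 5% vs 10% worsening), active: (0.80 + 0.825)/2 = 0.81.
- Benefit, placebo: (0.90 + 0.95)/2 = 0.93.

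The active-minus-placebo difference is negative in both.

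**The case against.** No two-sided p-value carries direction by itself. Step 2 shows that the signed test also returns p = 0.104 for mirror-image benefit and harm. That is correct, but with signed change the sign of the statistic gives the direction, and with the agreement score it does not. Nor does the general point answer the cancellation in the third table.

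Direction is visible elsewhere: the shift tables, the proportion in each stage and the proportion improving by at least one stage are all reported by arm. The SAP also calls the test one of agreement, not of improvement. This stands, and it limits the harm to a reader who looks only at the test.

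Protocol 9.4.7 with 9.4.6.1 already implies a stratified CMH test on the 1-stage improvement proportion, and SAP Section 8 does not withdraw it. The SAP's summary-only wording is a blanket sentence covering many endpoints. This also stands, so on that proportion the gap is a missing restatement. It does not repair the test the SAP does specify for change in stage.

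The power loss depends on assumed differential worsening. With none, the tests are equal. With equal 5% worsening, the agreement score does slightly better. The harm case is extreme: at 15% vs 5% worsening the agreement test rejects about 16% of the time, and at 20% vs 5% about 23%.

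The kappa slip is a separate matter, in code labelled as a template. The text is right and the template is wrong, so it needs correcting but adds nothing to the main point.

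**Conclusion.** The concern holds. As written, the only treatment test the SAP names for change in Hurley Stage does not test the signed endpoint that the SAP defines. The equal scoring of improvement and worsening follows directly from the formula and needs no assumption.

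The power cost does depend on assumptions. It ranges from nil when nobody worsens, through about 10 percentage points (71% vs 81%) at 5% vs 10% Stage II worsening, to about 38 points (51% vs 89%) at 5% vs 20%.

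The reach is narrow: one exploratory scale, assessed after baseline at Weeks 16, 32 and 40, of which only Week 16 is placebo-controlled. The other four shift-table scales have directional tests of their own. It should be corrected because the rule is wrong as written and the correction is small.

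**What to change.** 1. In SAP 7.5.3 and Appendix 2, for Hurley Stage at least, use signed change from baseline as the column score in the same Hurley-stratified CMH row-mean test, each dose against placebo. Keep the shift tables, and treat the agreement score and kappa as descriptive.
2. State in SAP 7.5.3 that the protocol's stratified CMH test applies to the proportion with at least a 1-stage improvement, or list its removal in SAP Section 8.
3. Correct the kappa template so that kappa comes from the baseline by post-baseline table within each arm, as the 7.5.3 text requires.

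The cost is one score variable, one TABLES statement and one or two sentences in the SAP. No data, visits or subjects are added.
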